1.1 AIM OF THE STUDY

The aim of this experimental study is to investigate the impact of hypoglycaemia on platelet activation parameters (PAP) during a hyperinsulinaemic hypoglycaemic clamp study.

1.2 STUDY HYPOTHESIS

Hypoglycaemia in patients with T2DM leads to increased platelet activation.

 endocrinology diabetology	Title: DIAPLATE-STUDY	Protocol No: Version 3.5	Sponsor: Medical University of Graz	Date: 13th February 2018
---	---------------------------------	------------------------------------	---	------------------------------------

2. OBJECTIVES AND OUTCOMES

2.1 PRIMARY OBJECTIVE

The primary objective is to investigate platelet activation during different levels of hypoglycaemia induced by a stepwise hyperinsulinaemic, hypoglycemic clamp experiment in patients with T2DM.

2.2 SECONDARY OBJECTIVES

To investigate

- Platelet activation and recovery at one week after the clamp experiment
- Changes of pro-atherothrombotic markers during the hypoglycaemic clamp
- Counter regulatory hormone response during the clamp

2.3 PRIMARY OUTCOME

- Changes in platelet activation measured by light transmittance aggregometry based on ADP activation from baseline to the end of the hypoglycaemia phase (i.e. 45 mg/dl for 30 minutes) (visit 3)

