4.3 WITHDRAWAL CRITERIA

Subjects may be withdrawn from the study at the discretion of the Investigator or Sponsor due to a safety concern or if judged non-compliant with trial procedures. A subject must be withdrawn from treatment if one of the following applies:

- Subject chooses to withdraw from the study at any time
- Pregnancy or intention of becoming pregnant during study duration
- Intolerable adverse effects
- Major violation of the study protocol
- Other circumstances that would endanger the health of the subject if he/she were to continue his/her participation in the trial

	Title: DIAPLATE-STUDY	Protocol No: Version 3.5	Sponsor: Medical University of Graz	Date: 13th February 2018
--	--------------------------	-----------------------------	--	-----------------------------

Reasons for withdrawals and discontinuation of any subject from the protocol have to be recorded.

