At approximately 07:00, two intravenous cannulas (catheters) will be inserted: one cannula will be inserted in an antecubital vein of a forearm for sampling of serial measurements of plasma glucose (approximately every 5-30 min, depending on the clamp procedure and safety). The hand will be placed in a heated environment to enable drawing of arterialised-venous blood. For controlled variable infusion of glucose 20% and infusion of human soluble insulin (40 IU Actrapid®, 100 IU/ml in 99.6 mL saline), an antecubital vein of the contralateral arm will be cannulated. Both cannulas will be kept open by a slow continuous 0.9% saline infusion. After the baseline blood samples for blood glucose, insulin, counter regulatory hormone parameters and platelet activity have been taken, the hyperinsulinemic hypoglycemic clamp will be started. A variable i.v. infusion of glucose 20% or infusion of human soluble insulin will be initiated in order to obtain a plasma glucose target of 5.5 mmol/L (100 mg/dL) \pm 10%. When the plasma glucose target of 5.5 mmol/L (100mg/dL) \pm 10% is reached the high constant insulin infusion (2.5 mU/kg/min) will be initiated. After 30 minutes the plateau 5.5mmol/L will be started. After 30 min on the 5.5 mmol/L plateau the glucose infusion will be interrupted, the PG will be allowed to decline to 3.5 mmol/L and by restarting the variable glucose infusion, kept stable at 3.5 mmol/L. Thereafter the glucose infusion will be interrupted and the PG will be allowed to decline to 2.5 mmol/L or a nadir at a higher concentration in case 2.5 mmol/L cannot be reached or symptoms of hypoglycaemia are unacceptable. By restarting the variable glucose infusion the PG will be kept stable at 2.5 mmol/L or nadir and assessments on the plateau will be performed. After 15 min on the 2.5 mmol/L or nadir plateau the constant high insulin infusion will be terminated. Starting at time point 25 min on the 2.5 mmol/L or nadir plateau the glucose infusion will be tapered off, if possible, to allow a spontaneous recovery from hypoglycaemia. PG will not be allowed to fall below 2.2 mmol/L. If PG has not reached 4.0 mmol/L 45 min after termination of the constant high insulin infusion, a constant high glucose infusion (5.5 mg/kg/min) will be initiated to increase PG to a level of 4.0 mmol/L. When reaching the PG level of 4.0 mmol/L assessments will be performed and blood samples will be taken. The PG will then be increased to 5.5 mmol/L for safety reasons and the clamp terminated, if deemed safe by the investigator. PAP and CRH samples will be obtained at the end of each plateau phase as well as after recovery from hypoglycaemia at PG 100mg/dl (see figure 1).

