
	Title: DIAPLATE-STUDY	Protocol No: Version 3.5	Sponsor: Medical University of Graz	Date: 13th February 2018
--	--------------------------	-----------------------------	--	-----------------------------

After initiation of the high constant insulin infusion potassium concentration will be measured at the discretion of the investigator and potassium replaced if necessary. ECG will be continuously monitored during the clamp procedure using patient cardiac monitoring system “Dräger”. One 12-lead ECG will be recorded during run-in phase (before starting constant high insulin infusion) and at hypoglycaemia or nadir of 2.5 mmol/L at approximately 15 min. In case a subjects PG does not decrease from 5.5 mmol/L to 3.5 mmol/L within 30 minutes, the 3.5 mmol/L assessment plateau will be initiated in any case after 30 minutes after the end of assessment plateau 5.5 mmol/L high insulin. In case a subjects PG does not decrease from 3.5 mmol/L to 2.5 mmol/L within 30 minutes, the 2.5 mmol/L assessment plateau will be initiated in any case after 30 minutes after the end of assessment plateau 3.5 mmol/L. In the above cases, the glucose infusion should not be initiated at the start of the assessment plateaus to allow a further decrease in PG levels to the scheduled target PG levels. Subjects will receive a meal and will remain at the study center until stabilisation of PG. When patients are in a normoglycemic state and in a good clinical condition, determined by the investigator, patients will be discharged home.

Figure 1. Hyperinsulinemic-Hypoglycemic Clamp with time points of sampling collection

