6.6. ADVERSE EVENTS RELATED TO THE CLAMP EXPERIMENT

The trial will include a hypoglycaemic clamp procedure during Visit 3. Within the clamp experiment hypoglycaemia is intentionally induced. Depending on potency of hypoglycaemia patients might feel discomfort, sweating, lack of concentration, dizziness, palpitations, or general discomfort. Hypoglycaemia will

	Title: DIAPLATE-STUDY	Protocol No: Version 3.5	Sponsor: Medical University of Graz	Date: 13th February 2018
--	--------------------------	-----------------------------	--	-----------------------------

be controlled by frequent venous glucose measurements. In case of unacceptable or unbearable hypoglycaemia during the clamp procedure, glucose will be administered and clamp investigation will be terminated if deemed necessary for the investigator or the subject wants to break up. During the entire clamp experiment, patients will be continuously monitored for glucose, heart rate, blood pressure and potassium. Medical staff is highly experienced and qualified for performing clamp investigations. The clamp may be interrupted or terminated for safety reasons at any time at the investigators discretion.

Independently from hypoglycaemia related adverse event, some discomfort may occur as a result from vein puncture or venous line issues. In some cases local haematoma can occur, very seldom installed venous lines might lead to local infection and phlebitis of the punctured vein which may require local and/or systemic treatment.

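### Does the primary paired t-test go wrong because subjects with unacceptable symptoms may stay at a higher nadir or have the clamp ended?

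*Combined protocol and SAP*

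**What the plan says.** Section 2.3 defines the primary outcome as the LTA change "from baseline to the end of the hypoglycaemia phase (i.e. 45 mg/dl for 30 minutes) (visit 3"). Section 7.2 tests it with a paired t-test, adjusted for variability seen at the euglycaemic clamp, and refers to a statistical analysis plan for details.

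Three places deal with a subject who does not tolerate or does not reach the target:

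- **Section 5.2.3 (Visit 3).** Glucose falls to 2.5 mmol/L "or a nadir at a higher concentration in case 2.5 mmol/L cannot be reached or symptoms of hypoglycaemia are unacceptable". The plateau is then held at that level and assessed, and "PAP and CRH samples will be obtained at the end of each plateau phase". If glucose falls too slowly, "the 2.5 mmol/L assessment plateau will be initiated in any case after 30 minutes after the end of assessment plateau 3.5 mmol/L".
- **Section 6.6.** "In case of unacceptable or unbearable hypoglycaemia during the clamp procedure, glucose will be administered and clamp investigation will be terminated if deemed necessary" by the investigator, or if the subject wants to stop.
- **Section 4.3.** "A subject must be withdrawn from treatment if one of the following applies"; the list includes "Intolerable adverse effects". It adds: "Reasons for withdrawals and discontinuation of any subject from the protocol have to be recorded".

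Section 7.1 sets 14 subjects, with enrolment up to 16 to cover drop-outs. For secondary endpoints, section 7.2 considers linear models for repeated measurements, including changes across the states of hypoglycaemia at Visit 3.

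**The concern.** The same kind of event, symptoms the subject cannot accept, can lead to two different data outcomes. On a higher nadir the subject is sampled and has a primary value. If the clamp is ended before the lowest-plateau sample, there is no pair and a paired t-test cannot use the subject. Nothing in the available text says how either group enters the primary analysis or names a sensitivity analysis.

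Such loss need not be random. Section 1 and section 5.3.7 plan to relate the counter-regulatory response to platelet activation. If stronger reactors also show more activation and are the ones lost, the estimate is too low and a real effect may be missed; if the link runs the other way, the estimate is too high. Replacing lost subjects up to 16 restores the count but not the kind of subject. The 45 mg/dl in the endpoint also cannot be literally true of a subject held at a higher nadir, so a strict reader might exclude that subject.

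**Working it through.** **1. The plan's own figure.** Inputs from section 7.1: difference 10, SD 12, two-sided 0.05, paired t-test. Power comes from the noncentral t distribution with n − 1 degrees of freedom and noncentrality (10/12)√n. This gives 78.8% at n = 13 and 82.2% at n = 14, so 14 is the smallest size reaching 80%. The sample size is not in dispute. For later comparison, n = 12 gives 74.8%, and the standard error at n = 14 is 12/√14 = 3.21.

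**2. Do the passages conflict?** Section 5.2.3 governs the glucose level at which the lowest plateau is held. Section 6.6 governs stopping, at any time, on the investigator's judgement or the subject's wish. Section 4.3 governs withdrawal from the study. They can all be followed together as steps of increasing severity. The first step keeps a symptomatic subject on a plateau with a sample. A clamp ended after that sample also still yields a pair.

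**3. Size of informative loss.** The documents give neither a loss rate nor a correlation, so this is an illustration under assumptions. Model: change = 10 + 12 × [ρS + √(1 − ρ²)e], with S (reaction) and e independent standard normal. The two subjects with the largest S are always lost and the rest are analysed by t-test (200,000 runs).

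| ρ | 16 enrolled, 2 lost: mean | power | 14 enrolled, 2 lost: mean | power |
|---|---|---|---|---|
| 0 | 10.0 | 82% | 10.0 | 75% |
| 0.3 | 9.2 | 77% | 9.1 | 68% |
| 0.5 | 8.7 | 74% | 8.5 | 65% |
| 0.7 | 8.2 | 71% | 8.0 | 62% |

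With the reserve used, the bias at ρ = 0.5 is 10 − 8.7 = 1.3, or 1.3/3.21 = 0.4 standard errors. At ρ = 0.3 it is 0.8, or about 0.25 standard errors. Without the reserve, 7 points of power (82% to 75%) go through sample size alone, before any selection; the reserve exists to cover that part.

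A cruder check gives the same order of size. If m of 14 subjects are lost and their true change differs from the completers' by x, the completer mean is off by xm/14. For m = 1 to 3 and x = 5 to 10 this runs from 5 × 1/14 = 0.4 to 10 × 3/14 = 2.1, in either direction.

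**4. Higher-nadir subjects.** Suppose 2 of 14 are off target and show a fraction f of the effect. Keeping them gives power of 66%, 71%, 76% and 82% for f = 0, 0.25, 0.5 and 1. Excluding them leaves n = 12 and 75%. The break-even is at about f = 0.46. Neither choice is better throughout, so power does not argue against the natural reading, which is to include everyone with the end-of-plateau sample.

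**5. What a sensitivity model would gain.** Take a likelihood model that also uses the 3.5 mmol/L sample, with 14 enrolled, 2 lost and ρ = 0.5. Bias falls from about −1.5 to between −0.5 and −0.9, depending on the assumed correlations. Root mean squared error falls from about 3.7 to between 3.4 and 3.5, since sampling error dominates. This assumes that every lost subject has the 3.5 mmol/L sample. The secondary outcomes in section 2.4 already include platelet parameters across states of hypoglycaemia, section 5.3.7 counts LTA among those parameters, and section 7.2 considers a repeated-measures model for them. Such a model can use a subject with early samples only.

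**The case for a change.** The best case for a change is that it costs little and that the trial is small. Each of 14 subjects carries weight, and who counts is best written down before data are seen. The loss is set off by the reaction itself, which is not ordinary drop-out, and the reserve cannot bring the lost reactors back. A named sensitivity analysis would need only samples already drawn.

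Part of this stands. The text would be clearer if it called 45 mg/dl the nominal target and said that every subject with the end-of-lowest-plateau sample is analysed. It is also true that a complete-pair analysis could be biased.

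The rest is weaker. The planned associations concern hormones and platelet activity; no passage links symptom tolerance to LTA. The simulation always removes the strongest reactors, which is an extreme mechanism. It also leaves out the euglycaemic-clamp adjustment in section 7.2, so its estimate is not quite that of the planned primary analysis. A sharper boundary between staying on the plateau and ending the clamp would have to be drawn inside a safety discretion that section 6.6 grants on purpose. Reasons for withdrawal and discontinuation must already be recorded under section 4.3, so early endings can be counted and explained. Relabelling a model already under consideration would leave the primary test as it is.

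**Conclusion.** No change follows. This is a gap in detail that an analyst would fill sensibly: include every subject with a baseline and an end-of-lowest-plateau sample, treat 45 mg/dl as the target level, report the clamps that ended early with their reasons, and read the primary result beside the repeated-measures analysis across plateaus.

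Under assumptions chosen to make the problem visible (2 of 16 lost, always the strongest reactors, correlation 0.5), the bias is about 1.3 LTA points against a standard error of 3.2, and power falls from 82% to 74%. With no such correlation, or with no clamps ended before the sample, the bias is zero. The documents settle neither its size nor its direction, and they do not show that the paired t-test with the reserve to 16 would give a wrong answer. The separate statistical analysis plan named in section 7.2 and the content of Figure 1 were not available, so the missing detail may be given there.

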2.4 SECONDARY OUTCOMES

- Changes in platelet activation measured by activation marker, such as CD62P, CD63 and PAC1, on CD41^{pos} or CD42b^{pos} platelets from baseline to the end of the hypoglycaemia phase
- Changes in platelet activation measured by activation marker, such as LTA, CD62P, CD63 and PAC1, on CD41^{pos} or CD42b^{pos} platelets from the end of the hypoglycaemic clamp to one day after the clamp
- Changes in platelet activation measured by activation marker, such as LTA, CD62P, CD63 and PAC1, on CD41^{pos} or CD42b^{pos} platelets from the end of the hypoglycaemic clamp to one week after the clamp
- Changes in platelet activation measured by PFA-100 from baseline to the end of the hypoglycaemia phase
- Changes in platelet activation measured by PFA-100 from the end of the hypoglycaemic clamp to one day and one week after the clamp
- Changes in interleukin-6 (IL-6), von Willebrand factor [vWF], plasminogen activator inhibitor (PAI-1), vascular adhesion molecule (VCAM) and intercellular adhesion molecule (ICAM) from baseline to the end of the hypoglycaemia phase
- Changes in interleukin-6 (IL-6), von Willebrand factor [vWF], plasminogen activator inhibitor (PAI-1), vascular adhesion molecule (VCAM) and intercellular adhesion molecule (ICAM) from the end of the hypoglycaemic clamp to one week after the clamp
- Difference of platelet activation parameters during different states of hypoglycaemia
- Counter regulatory hormone response during hypoglycaemia

	Title: DIAPLATE-STUDY	Protocol No: Version 3.5	Sponsor: Medical University of Graz	Date: 13th February 2018
--	--------------------------	-----------------------------	--	-----------------------------

3. STUDY DESCRIPTION

3.1 DESIGN

Monocentric, single arm, open, mechanistic trial to evaluate the effect of hypoglycaemia on PAP.

3.2 DURATION OF STUDY

Active study duration will be 5 days for each study participant.

4. STUDY POPULATION

We will study 14 subjects with T2DM without history of cardiovascular events or manifest atherosclerosis.

4.1 INCLUSION CRITERIA

- Male or female aged 18-64 years (both inclusive) at the time of signing informed consent
- Subjects diagnosed with type 2 diabetes (diagnosed regarding WHO criteria) and on stable treatment for a period of 90 days prior to screening with metformin as monotherapy or diet only. Stable is defined as unchanged dose
- Body mass index (BMI) between 20.0 and 35.0 kg/m² (both inclusive)
- HbA1c between 43 and 64 mmol/mol (6.0% – 8.0%) (both inclusive)
- No use of platelet inhibiting therapy (e.g. aspirin, clopidogrel, ticagrelor, prasugrel)

4.2 EXCLUSION CRITERIA

- All other forms of diabetes (type 1 diabetes, gestational diabetes) than type 2 diabetes mellitus
- Treatment with any glucose lowering agent(s) other than metformin in a period of 60 days before screening. An exception is short-term treatment (\leq 7 days in total) with insulin due to intercurrent illness
- Impaired hypoglycaemic awareness determined at the discretion of the investigator
- Medical history of arrhythmia as atrial fibrillation, atrial flutter, atrioventricular dissociation disorders or ventricular arrhythmias
- Previously known cardiovascular disease and / or past cardiovascular events, or past episodes of a congestive heart failure syndrome (NYHA II - NYHA IV)
- Severe hypoglycaemic event requiring third party help in the last 6 months
- Known allergy to human insulin or dextrose solution
- Clinically significant abnormal haematology, biochemistry, lipids, hormones, coagulation or urinalysis

 endocrinology diabetology	Title: DIAPLATE-STUDY	Protocol No: Version 3.5	Sponsor: Medical University of Graz	Date: 13th February 2018
---	--------------------------	-----------------------------	--	-----------------------------

- Uncontrolled hypertension defined as resting blood pressure at screening (after resting for 5 min, measured in sitting position) outside the range of 90–160 mmHg for systolic or 50–100 mmHg for diastolic
- Chronic liver failure with severe liver dysfunction as assessed by the investigator
- ALT or AST levels > 3x ULN
- eGFR <45 ml/min/1,73 m²
- Any musculoskeletal disorders holding back from stay in bed in a lying position during the time of the clamp experiments
- Treatment with beta-blockers, antiarrhythmic agents or neuroleptic drugs
- Active smoker or intake of illicit substances
- Regular intake of NSAR/NSAIDs
- Any mental disorders or psychiatric conditions which may interfere with understanding or conduction of study related procedures
- Females of child bearing potential without adequate contraceptive methods (i.e. sterilisation, intrauterine device, vasectomised partner; or medical history of hysterectomy)

Exclusion from clamp investigation:

- Treatment with NSAR/NSAID or metamizole within 10 days prior to clamp visits
- Fasting plasma glucose >9.0 mmol/l (>162 mg/dl) on the day of clamp investigation

If one of these exclusion criterial for the clamp visits is met, the clamp visit will be postponed for 10-15 days.

4.3 WITHDRAWAL CRITERIA

Subjects may be withdrawn from the study at the discretion of the Investigator or Sponsor due to a safety concern or if judged non-compliant with trial procedures. A subject must be withdrawn from treatment if one of the following applies:

- Subject chooses to withdraw from the study at any time
- Pregnancy or intention of becoming pregnant during study duration
- Intolerable adverse effects
- Major violation of the study protocol
- Other circumstances that would endanger the health of the subject if he/she were to continue his/her participation in the trial

	Title: DIAPLATE-STUDY	Protocol No: Version 3.5	Sponsor: Medical University of Graz	Date: 13th February 2018
--	--------------------------	-----------------------------	--	-----------------------------

Reasons for withdrawals and discontinuation of any subject from the protocol have to be recorded.

4.4 TERMINATION OF THE ENTIRE TRIAL

Premature termination of the clinical trial will be considered if the sponsor believes it is necessary to terminate the clinical trial for safety reasons, or when the clinical trial proves to be impracticable.

5. VISIT PROCEDURES, MEASUREMENTS AND ASSESSMENTS

5.1 RECRUITMENT AND SCREENING

The site will recruit potential subjects by using an available local recruitment registry. No study-related procedures are undertaken before obtaining informed consent. The study team will explain in detail the study procedures and asks the participant about his/her willingness to participate in this research study. After informed consent is signed and obtained, participants are given a signed copy of the informed consent document and are assigned a screening identification number in ascending order starting with "01".

After obtaining informed consent at the screening visit, subject's eligibility will be further assessed and documented by using a source data form (SDF) with a list of inclusion and exclusion criteria, medical history (including all medications past and current) will be acquired and the following measurements will be performed: body weight, height, blood pressure, electrocardiography, pregnancy test, blood parameters (see Table1, including Hepatitis B, C and HIV-Test).

Subjects unable to provide written informed consent will not be included in the study.

A summary of all visits and procedures has been outlined below (table 1). A more detailed description of each visit and accompanying procedures can be found under section 5.2

	Title: DIAPLATE-STUDY	Protocol No: Version 3.5	Sponsor: Medical University of Graz	Date: 13th February 2018
--	--------------------------	-----------------------------	--	-----------------------------

